## Clinical Investigation Plan

Automatic Control of Total Intravenous Anesthesia: Closed-loop Delivery of Propofol and Remifentanil Using Bispectral Index as Feedback Variable.

Acronym: ACTIVA 2. Id code: NP-2861. NCT number: NCT04432974.

- Single-use sterile PVC extension lines (1mm) with a length of 200 cm, male-to-female, with a ring.
- Single-use, sterile, latex-free infusion kits.
- Single-use, latex-free BIS Quatro sensors.

### Purpose of use for the experimental device

The target population for the device consists of surgical patients undergoing elective procedures requiring general anesthesia, and for whom intravenous anesthesia is advantageous. The ACTIVA software is programmed to operate exclusively during intravenous anesthesia when propofol is administered as a hypnotic agent and remifentanil as an analgesic. The experimenters must be specialists in anesthesia and intensive care with adequate knowledge of the operation of the ACTIVA software and its GUI. In particular, familiarity with the user manual is required. The primary experimenter is responsible for training the experimenters in the use of the ACTIVA software before its clinical application and for providing guidance during the clinical investigation until the experimenters achieve complete autonomy in using the ACTIVA software.

[figure not shown]

Figure 1: Schematic representation of the infusion system for anesthetic drugs based on the ACTIVA software.

### Clinical Investigation Plan

Automatic Control of Total Intravenous Anesthesia: Closed-loop Delivery of Propofol and Remifentanil Using Bispectral Index as Feedback Variable.

Acronym: ACTIVA 2. Id code: NP-2861. NCT number: NCT04432974.

[figure not shown]

Figure 2: Graphical User Interface (GUI) of the ACTIVA software.

### Number of experimental medical devices expected to be used

It is expected to use a single experimental medical device.

### Risks and benefits of the medical device

The sponsor is responsible for evaluating the safety of the medical device under investigation in the clinical trial, reviewing recorded adverse events, conducting investigations into unforeseen serious adverse events, and notifying the regulatory authorities as per applicable regulations. The sponsor is also responsible for training investigators prior to the commencement of the study, including reporting of serious adverse events. The sponsor will oversee the procedures for adverse events related to the clinical investigation and may assist investigators in the medical review of reported adverse events. The principal investigator is responsible for ensuring the safety and health of enrolled subjects and must report adverse events to the manufacturer, the relevant ethics committee, and the investigational site. The investigator must provide all necessary information for the completion of the adverse event form at the investigational site. The principal investigator is responsible for reporting a serious adverse event to the Ethics Committee and the relevant regulatory authority according to local regulations. The investigator must assist the sponsor and the manufacturer in the clinical review of the adverse event, providing all available documentation. The sponsor and the principal investigator are obligated to inform other investigators, regulatory authorities, and the ethics committee of the serious adverse event in accordance with local regulations.

### Expected clinical benefits

The medical device ACTIVA, the subject of the clinical investigation, has been developed to be reliable, safe for the patient, and clinically effective. Specifically, the device is designed to be user-friendly through its user-friendly (GUI).

### Clinical Investigation Plan

Automatic Control of Total Intravenous Anesthesia: Closed-loop Delivery of Propofol and Remifentanil Using Bispectral Index as Feedback Variable.

Acronym: ACTIVA 2. Id code: NP-2861. NCT number: NCT04432974.

In a clinical setting, the medical device should be effective in maintaining the enrolled subject within the desired hypnosis range (BIS between 40 and 60), minimizing periods during which the enrolled subject exhibits anesthesia levels that are either too shallow or too deep.

### Predicted clinical risks associated with the device and residual risks

The clinical risk associated with the use of the ACTIVA software should not exceed the clinical risk associated with manual control (standard of care). In cases where the results obtained during simulations are not replicated in a clinical setting, it is possible that the software may fail to ensure adequate levels of anesthesia. The principal investigator will decide to interrupt the system and switch to manual mode (current standard of care).

The clinical investigation of the ACTIVA software is the first of its kind for the system, where anticipated adverse events related to the device and risk analysis are the primary focus of this clinical study. During the software development, the primary objective was to eliminate/minimize these risks.

To minimize device-related risks, the ACTIVA software cannot be initiated if the connected devices are not functioning correctly (refer to the user manual). The proper functioning of the control software and its components is indicated on the graphical user interface with a green light, allowing the principal investigator to promptly assess the system's correct operation.

Although the device has undergone extensive testing and simulations during its development, it is possible for it to stop functioning during use. Therefore, the ACTIVA software must be under constant supervision by the investigator, who can detect malfunctions or anomalies through the graphical user interface and take prompt action.

In particular, simulation tests have been conducted to verify that the ACTIVA control system can be interrupted and switched to manual mode (standard of care) in less than 20 seconds. This time period is shorter or overlapping with the time it takes for an anesthesiologist to manage a normal infusion pump that needs to be turned off and restarted and much shorter than the time required to replace a malfunctioning infusion pump.

In the event of a malfunction during drug infusion, the ACTIVA software is capable of promptly alerting the investigator by emitting appropriate auditory and visual signals (red light) on the graphical interface and auditory signals directly from the infusion pumps. Additionally, the investigator can easily and quickly switch to manual control mode for the pumps (see user manual). Examples of malfunctions may include:

- Software freeze/crash.
- Data transmission malfunctions.
- Infusion pump malfunctions.

The ACTIVA software always generates a report file, even in the case of malfunctions, containing all the data from patient monitoring, infusion pumps, and the software itself, along with notes entered by the principal investigator. Through data analysis, it is possible to identify the source of the technical issue.

In the event of ACTIVA software malfunction, the patient monitoring systems, particularly the Bispectral Index (BIS), are never altered or damaged (the data flow is only outbound to the computer where the ACTIVA software is installed), while the infusion pumps continue to operate in manual mode (standard/classic mode controlled by the anesthesiologist).

Switching to manual control is always possible at the discretion of the principal investigator, even in the absence of system malfunctions.

### Clinical Investigation Plan

Automatic Control of Total Intravenous Anesthesia: Closed-loop Delivery of Propofol and Remifentanil Using Bispectral Index as Feedback Variable.

Acronym: ACTIVA 2. Id code: NP-2861. NCT number: NCT04432974.

## Risks associated with participation in the clinical investigation

The investigator monitors the system to prevent any consequences for the enrolled subject in the clinical investigation in case the reliability and safety of the system are compromised. From a clinical perspective, it is possible for the software to provide stable and adequate anesthesia. The investigator may choose to switch to manual control if this is not the case.

The drugs Propofol and Remifentanil have received marketing authorization and are standard of care for intravenous general anesthesia. The ACTIVA software does not increase the known risks associated with the infusion of these drugs.

The pumps and the monitor are not altered in their original functions by the software; therefore, the risks associated with these devices are not increased.

## Interaction with concurrent medical treatments

The ACTIVA control system does not interfere in any way with the surgical procedure, and therefore, there are no surgical risks attributable to the control system.

During intravenous general anesthesia, medications that interact with the anesthetic drugs Propofol and Remifentanil may be administered for clinical reasons. This also occurs during the operation of the ACTIVA software. There are no additional risks compared to normal clinical practice regarding these interactions.

## Procedures for risk control or reduction

For patient safety, approval must be obtained from the competent ethics committee for the investigational site, as well as authorization from the investigational site.

Investigators will be trained by the principal investigator and the manufacturer to ensure a clear understanding of the protocol, user manual, and all relevant study processes.

Each investigator will be registered on a list of investigators, which will be signed, expressing their commitment to conducting the study according to the protocol, recording the required data, and maintaining continuous supervision over the device.

A dedicated advisory board has been established to continuously assess subject safety and the suitability of the ACTIVA software to continue the clinical investigation. The group's responsibility also includes suggesting to the sponsor whether to continue or terminate the clinical investigation.

Risks are minimized by adhering to the protocol, using the device according to the user manual, following the hospital procedures of the sponsor's site, adhering to subject selection criteria, and maintaining constant supervision of the subject and ACTIVA software through the graphical user interface.

## Risks/benefits ratio

The ACTIVA software should prove to be safe, reliable, and feasible. Furthermore, considering that the sample size of the study is calculated based on the clinical evaluation of the infusion system, it is possible that it will demonstrate the ability to maintain an optimal level of anesthesia compared to what is described in the literature for other similar systems and better than the standard of care.

## Clinical Investigation Plan

Automatic Control of Total Intravenous Anesthesia: Closed-loop Delivery of Propofol and Remifentanil Using Bispectral Index as Feedback Variable.

Acronym: ACTIVA 2. Id code: NP-2861. NCT number: NCT04432974.

## Information related to the clinical investigation

### Clinical study objectives

The primary objective of the clinical investigation is to investigate the clinical performances obtainable by the control system under study in terms of depth of hypnosis adequacy.

The secondary objective is to evaluate the reliability, safety and applicability of the control system under study and to carry out the clinical evaluation of the automatic control system during the induction, maintenance and recovery of general intravenous anesthesia.

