## Number of patients enrolled

The sample size was determined based on the primary outcome measure concerning the depth of hypnosis adequacy provided by the ACTIVA control software. Specifically, it was calculated with the aim to assess the proportion of patients for whom the percentage of the anesthesia maintenance duration in which the BIS is kept inside the recommended range from 40 to 60 is greater than 43%. This latter value is the average percentage that was observed in a previous data acquisition campaign concerning manually controlled TIVA, which was performed in the same clinical setting considered for the present clinical trial (Study acronym: ACTIVA 1, Id code: NP-1843).

The proportion was estimated to be 90% of patients with a 95% confidence interval and a margin of error of 10%. The resulting sample size is 139 patients. This number of enrolled subjects also ensures that the ACTIVA control software is adequately tested for safety, reliability, feasibility, and applicability. Secondary outcome measures were not considered in the sample size calculation.

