Statistical Analysis Plan

Study title	Automatic Control of Total Intravenous Anesthesia: Closed-loop Delivery of Propofol and Remifentanil Using Bispectral Index as Feedback Variable. Acronym: ACTIVA 2.
Identifier code of the clinical investigation	NP-2861
Version number of the clinical investigation	Version 4
Version date	07/03/2019
NCT number	NCT04432974
Sponsor	Azienda Socio Sanitaria Territoriale degli Spedali Civili di Brescia
Principal investigator	[name] Medical specialist in anesthesia and intensive care medicine at the 2nd Department of Anesthesia and Intensive Care, ASST Spedali Civili di Brescia.
Location	Azienda Socio Sanitaria Territoriale degli Spedali Civili di Brescia, 25123, Brescia, Italy.
Author of the document	[name]
Document date	17/06/2020

Statistical Analysis Plan

Automatic Control of Total Intravenous Anesthesia: Closed-loop Delivery of Propofol and Remifentanil Using Bispectral Index as Feedback Variable.
Acronym: ACTIVA 2. Id code: NP-2861. NCT number: NCT04432974.

Index

List of abbreviations.....	3
Introduction.....	3
Study design.....	4
Sample size calculation.....	5
Aims and objectives.....	5
Outcomes.....	5
Population to be analyzed.....	6
Analyses.....	7
Data management.....	8

Statistical Analysis Plan

Automatic Control of Total Intravenous Anesthesia: Closed-loop Delivery of Propofol and Remifentanil Using Bispectral Index as Feedback Variable.

Acronym: ACTIVA 2. Id code: NP-2861. NCT number: NCT04432974.

List of abbreviations

ACTIVA = automatic control of total intravenous anesthesia;

BIS = bispectral index scale;

GUI = graphical user interface;

HR = heart rate;

MBP = mean blood pressure;

PONV = postoperative nausea and vomiting.

Introduction

This study concerns the clinical evaluation of a closed loop control system for the automatic administration of anesthetic drugs in TIVA (Total Intravenous Anesthesia). The purpose of the experimentation is to demonstrate that the control system under study is reliable, safe, applicable and capable of inducing and maintaining an optimal anesthetic level.

Statistical Analysis Plan

Automatic Control of Total Intravenous Anesthesia: Closed-loop Delivery of Propofol and Remifentanil Using Bispectral Index as Feedback Variable.

Acronym: ACTIVA 2. Id code: NP-2861. NCT number: NCT04432974.

Study design

The clinical study ACTIVA 2 is a pragmatic, interventional, nonrandomized, single-arm, single-center.

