¹ Burst suppression is defined as a period on the electroencephalogram trace characterized by attenuated or suppressed signal (<10 mV) alternating with brief periods of cortical activity, precisely termed 'bursts.' More than 50% of this period is dominated by attenuated/suppressed activity. This effect may sometimes be intentionally induced, for example, during neuroanesthesia, as a protective measure against cerebral ischemia, as it coincides with a reduction in cerebral metabolism. However, it is important to consider that it is also associated with a higher incidence of postoperative delirium.

Statistical Analysis Plan

Automatic Control of Total Intravenous Anesthesia: Closed-loop Delivery of Propofol and Remifentanil Using Bispectral Index as Feedback Variable.

Acronym: ACTIVA 2. Id code: NP-2861. NCT number: NCT04432974.

The following data are collected by the principal investigator after surgery and noted on the patient's anesthesiology clinical record form.

- System dysfunctions.
- Level of satisfaction of the experimenter.
- HR.
- MBP.
- Postoperative sedation.
- PONV.
- Postoperative analgesia.

Descriptive statistics will be performed on all study variables.

Quantitative data will be presented as mean (SD) or median (IQR) according to their distribution. Normality of the data will be tested using a Shapiro-Wilk test. Categorical data will be presented as frequency (proportion).

Data management

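### Safety is a stated objective, but no incidence of adverse events or switches to manual control is prespecified, and the claim that 139 patients test safety adequately has no calculation behind it

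*Protocol*

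**What the plan says.** Four statements set up the safety claim.

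- Protocol, *Clinical study objectives*: "The secondary objective is to evaluate the reliability, safety and applicability of the control system under study". The clinical evaluation in the same objective covers induction, maintenance and recovery. The SAP, *Aims and objectives*, repeats it.
- SAP, *Introduction*: "The purpose of the experimentation is to demonstrate that the control system under study is reliable, safe, applicable".
- Protocol, *Predicted clinical risks associated with the device and residual risks*, which describes the study as the first clinical investigation of the system: "anticipated adverse events related to the device and risk analysis are the primary focus of this clinical study".
- Protocol, *Number of patients enrolled*, repeated in the SAP's *Sample size calculation*: "This number of enrolled subjects also ensures that the ACTIVA control software is adequately tested for safety, reliability, feasibility, and applicability". The next sentence reads: "Secondary outcome measures were not considered in the sample size calculation".

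The planned analysis is one line in the SAP, *Analyses*: "Descriptive statistics will be performed on all study variables". It adds only the choice between mean (SD) and median (IQR), a normality test, and frequencies for categorical data.

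**The concern.** An objective needs an outcome and an analysis that can answer it. The usual evidence on device safety is how many patients had an adverse event, how many had a serious or device-related one, and how often the clinician had to take over. None of these is named as a trial result in either document. A report that followed the plan could conclude that the system is safe without stating one event rate or its upper limit. It could also cite the sample-size paragraph as assurance that safety had been adequately tested, although that paragraph contains no safety calculation.

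**Working it through.** **1. Where 139 comes from.** Inputs from *Number of patients enrolled*: expected proportion p = 0.90, 95% confidence, margin of 10%. Formula: n = z²·p(1−p)/h², with z² = 3.8415.

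- h = 0.05 (total interval width 10 points): 3.8415 × 0.09 / 0.0025 = 138.29, rounded up to 139. This matches.
- h = 0.10 (±10 points): 3.8415 × 0.09 / 0.01 = 34.57, rounded up to 35. This does not match.

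So 139 is the precision of the BIS proportion at ±5 points, with no safety input. (The wording of the margin is a separate matter.)

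**2. What is listed, and what is not.** I compared the outcome lists (Protocol, *Clinical study description*; SAP, *Outcomes*), the variable lists (Protocol, *Measured variables*; SAP, *Analyses*) and the analysis sections.

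- Present and relevant to safety: number and types of dysfunctions; percentage of maintenance with HR below 50, MBP below 65 mmHg or BIS below 40; postoperative HR, MBP, sedation, PONV and pain; recorded oxygen saturation and burst suppression ratio.
- Absent: the number of patients with any adverse event, any serious adverse event, any device-related event or any switch to manual control; any safety criterion or threshold.

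The SAP line on all study variables does not bring in the absent items, because they are not listed as study variables.

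**3. Limits of what is present.**

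- Maintenance is defined as starting when induction ends, so the HR and MBP percentages leave out automated induction, which the objective includes.
- Dysfunctions do not count every switch. The protocol allows a switch without any malfunction (*Predicted clinical risks*, *Instrument-phenomenon interaction*, *Factors that may compromise the outcome and interpretation of the results*).
- Three inclusion rules apply to patients stopped early. *Subject Enrollment Count* has all available data analysed if the patient discontinues while the software is running. *Deviations from the clinical evaluation plan* removes from the secondary outcomes those who do not complete because of software issues or investigator discretion. *Selection bias at the time of analysis* leaves it to the experimenter whether data up to an interruption are included. The SAP's *Population to be analyzed* settles none of this.

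**4. What 139 patients could show.** With 0 events in n patients, the exact upper limit is 1 − 0.025^(1/n) two-sided, or 1 − 0.05^(1/n) one-sided.

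- n = 139: 1 − 0.025^(1/139) = 2.6%; 1 − 0.05^(1/139) = 2.1%.
- n = 130, if fewer start: 1 − 0.025^(1/130) = 2.8%.

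The documents give no event rate, so the true rates here are assumed. The chance of seeing no event in 139 is:

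- 0.1%: 1 − 0.13 = 87%
- 0.5%: 1 − 0.50 = 50%
- 1%: 0.99^139 = 25%
- 2%: 0.98^139 = 6%
- 5%: 0.1%

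For a 95% chance of seeing at least one event at a true rate of 1%, n = ln 0.05 / ln 0.99, rounded up to 299.

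**5. Effect of the exclusion rule (assumed numbers).** Suppose 7 of 139 patients had an event, all 7 were stopped for software problems, and all 7 were removed. The secondary set would show 0/132, upper limit 1 − 0.025^(1/132) = 2.8%. The full count would be 7/139 = 5.0%, with an exact 95% upper limit of 10.1%.

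**The case against.** The strongest reply is that safety evaluation is not missing. PONV is itself an adverse effect and is a named outcome. Time with BIS below 40 bears directly on overdosing, and oxygen saturation and burst suppression are recorded every second. Outside the SAP, the sponsor reviews recorded adverse events (*Risks and benefits of the medical device*), an advisory board assesses subject safety continuously (*Procedures for risk control or reduction*), safety notes are analysed monthly (*Clinical investigation monitoring plan*), and the final report must critically evaluate all data (*Declaration of Compliance*). Switches caused by malfunction would largely appear as dysfunctions, and discretionary ones are noted in the report file.

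All of this stands, and it rules out three stronger readings that a reader might infer.

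- That safety would be judged on heart rate, blood pressure and dysfunctions alone, or that nothing said about safety could be supported. The outcomes above will give some evidence.
- That 139 is too few. The documents set no event rate or threshold to be excluded, so a 2.6% limit shows that the statement is unquantified, not that the sample is inadequate.
- That adverse events are the trial's primary outcome. The sentence about primary focus is in the risk section and concerns anticipated device-related events and risk analysis. The objectives section makes depth of hypnosis primary and safety secondary.

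What the reply does not supply is a prespecified incidence, with a denominator and an interval, for events or switches. Recording, review and reporting do not define a trial result.

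**Conclusion.** The point holds in this form: safety is a secondary objective that the SAP aims to demonstrate, but no incidence of adverse events, serious adverse events or switches to manual control is prespecified. The planned safety-related outcomes give limited evidence, because the HR and MBP percentages omit induction and one inclusion rule removes patients stopped for software issues or at the investigator's discretion. The assurance attached to 139 is unjustified, since the same paragraph says that secondary outcomes played no part in the sizing. At best, 139 patients with no events exclude rates above 2.6% (two-sided) or 2.1% (one-sided). These limits assume that all 139 start ACTIVA control and are counted; the chances of missing an event rest on assumed rates. The plan should be changed on this point, but the gap does not invalidate the primary outcome.

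**What to change.** 1. Add a safety table to the SAP for all patients in whom ACTIVA control was started: number and percentage with any adverse event, any device-related event, any serious adverse event and any switch to manual control, with malfunction-driven and discretionary switches shown separately. Give each an exact 95% confidence interval. State the event definition, how device-relatedness is judged and the collection window, none of which the documents give.
2. Reconcile *Subject Enrollment Count*, *Selection bias at the time of analysis* and *Deviations from the clinical evaluation plan*, so that patients stopped early stay in this table, and carry the rule into the SAP.
3. Replace the assurance about safety testing in the protocol's *Number of patients enrolled* and the SAP's *Sample size calculation* with: *The sample size was not based on safety; if 139 patients start ACTIVA control and no event is seen, the exact two-sided 95% upper limit for the event rate is 2.6%.* Recompute it for the number who actually start, for example 2.8% for 0/130.

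Cost: no new patients or visits. The adverse event form, the recording of serious events and the notes of interruptions are already required. The extra work is one table, the definitions behind it and the reworded text. The safety statement also becomes less favourable.
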